9.4.5. Safety Analyses

All safety analyses will be performed on the Safety Analysis Set. Safety analyses will be descriptive; no formal statistical testing will be performed. These analyses will be performed as outlined below, with further details provided in the SAP.

Adverse events:

All AEs will be mapped to SOC and PT using the MedDRA classification system. The participant incidence of AEs, AEs related to study intervention, SAEs, AEs leading to discontinuation, and fatal AEs will be summarized. This overall summary will also provide AEs by maximum severity. Note summaries will be provided by treatment group, study period, and time of onset.

The participant incidence of AEs, AEs related to study intervention, and AEs leading to discontinuation will also be presented by SOC and PT. Preferred term summaries may also be provided.

If a participant has multiple events with the same PT occurring in different study periods, the event will be reported for each of those periods. Multiple increases in severity will be counted as 1 AE.

Vital signs:

For each vital sign parameter, summary statistics will be provided for observed and change from Baseline values by scheduled visit.

Physical examinations:

Observed and change from Baseline values for weight will be summarized descriptively by scheduled visit.

12-lead ECG:

Observed and change from Baseline values for ECG intervals will be summarized descriptively. QT abnormalities will be assessed; the number and proportion of participants with values or change from Baseline values exceeding certain thresholds will be tabulated.

Laboratory evaluations:

Observed and change from Baseline laboratory evaluations will be summarized descriptively. Markedly abnormal laboratory findings will be summarized separately.

C-SSRS and QUIP-RS:

The CSSRS parameters and QUIP-RS scores will be summarized descriptively by scheduled visit.

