8.3.7. Questionnaire for Impulsive-Compulsive Disorders in Parkinson's Disease Rating Scale

The QUIP-RS is a rating scale designed to measure the severity of, and support a diagnosis of, impulse control and related disorders in PD. It can also be used to monitor changes in symptom severity over time ([Weintraub, 2012](#)).

The QUIP-RS is a brief, self-rated questionnaire. It consists of 4 primary questions (pertaining to commonly reported thoughts, urges/desires, and behaviors associated with ICDs), each applied to the 4 ICDs (gambling, sex, buying, and eating) and 3 related disorders (hobbyism, punding, and medication use). It uses a 5-point Likert scale (scored 0 [never] to 4 [very often] for each question) to gauge the frequency of behaviors.

A copy of the QUIP-RS is found in the Trial Site Binder.

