### 4.1. General Considerations

Unless otherwise specified, continuous data will be summarized using descriptive statistics comprising of the number of participants with data to be summarized (n), mean, standard deviation (SD), median, minimum (min) and maximum (max). Categorical variables will be summarized as frequency and proportion.

Summaries will present the treatment groups in the following order: Placebo, JZP385.

For outputs summarized under Full Analysis Set and mITT, participants will be analyzed according to the randomized treatment arm. For outputs summarized under the Safety Analysis Set [REDACTED], to handle potential drug dispensation error(s), the actual treatment arm will be mapped according to the most frequently dispensed IMP taken by participants.

All summaries, statistical analysis, data listings, and figures will be generated using SAS version 9.4 (SAS Institute, Inc. Cary, NC) or higher. Each summary, figure, or data listing will include the data cutoff date in addition to the production date.

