**Table 7: Visit Windows Mapping for Assessments**

Study Period	Scheduled Visit	Target Study Day	TETRAS-ADL /TETRAS-PS, PGI-S/CGI-S, MDS-UPDRS	PGI-C/CGI-C	█████████████████████ Weight, ██████████ QUIP-RS	Chemistry, Hematology, Urine Drug Screening	Temperature and Respiratory rate, Urinalysis Labs	ECG	Blood Pressure and Pulse, C-SSRS
Screening	Screening	na	Any Day up to -2	na	Any Day up to -2	Any Day up to -2	Any Day up to -2	Any Day up to -2	Any Day up to -2
Baseline	Baseline	-1	Closest prior to dosing	na	Closest prior to dosing	Closest prior to dosing	Closest prior to dosing	Closest prior to dosing	Closest prior to dosing
DTOP	Week 1	7	na	na	na	na	1 – 20	1 – 34	1 – 10
	Week 2	14	na	na	na	na	na	na	11 – 20
	Week 5	35	1 – 48	na	na	1 – 48	21 – 48	na	21 – 48
MTP*	Week 9	63	49 – 76	1 – 76	na	49 – 76	49 – 76	35 – 90	49 – 76
	Week 13	91	77 – 104	77 – 104	na	77 – 104	77 – 104	na	77 – 104
	Week 17	119	105 – End of MTP	105 – End of MTP	36 – End of MTP [**or >36 and not SFU visit]	105 – End of MTP	105 – End of MTP	91 – End of MTP	105 – End of MTP
SFUP	Safety Follow-up	na	Nominal SFU visit	na	Nominal SFU visit [weight and QUIP-RS only]	Nominal SFU visit	Nominal SFU visit	Nominal SFU visit	Nominal SFU visit

Abbreviations: CGI-C = Clinician's Global Impression of Change; C-SSRS = Columbia Suicide Severity Rating Scale; DTOP = Dose Titration and Optimization Period; ECG = electrocardiogram; [REDACTED] MDS-UPDRS = Movement Disorder Society Unified Parkinson's Disease Rating Scale; MTP = Maintenance Period; PGI-C = Patient's Global Impression of Severity; PGI-S = Patient's Global Impression of Change; [REDACTED] QUIP-RS = Questionnaire for Impulsive-Compulsive Disorders in Parkinson's Disease Rating Scale; [REDACTED] SFUP = Safety Follow-up Period; TETRAS = The Essential Tremor Rating Scale.

\* In case of early discontinuation, Efficacy follow-up visits will be considered as scheduled visit, see Protocol, Section 7.1.1

\*\* For participants who don't enter the MTP, assessments (different from safety follow-up) occurring 36 days post first dose date will be mapped to Week 17.

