#### **4.6.3.6. Questionnaire for Impulsive-Compulsive Disorders in Parkinson's Disease Rating Scale**

Questionnaire for Impulsive-Compulsive Disorders in Parkinson's Disease Rating Scale (QUIP-RS) conducted at Baseline and Week 17 will be summarized at each visit for 4 ICDs (gambling, sex, buying, and eating), 3 related disorders (hobbyism, punding, and medication use), as well as the total QUIP-RS score. Higher scores signify a higher magnitude of the impact of impulse control disorders.

A listing will be created for all individual questions as well as summary scores of 4 ICDs, 3 related disorders and the total score.

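### QUIP-RS, a named safety endpoint, is tabulated only as observed scores by visit, with no within-participant change and no by-arm count of participants who worsen

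*Protocol*

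**What the plan says.** QUIP-RS is listed in the endpoint for the safety objective (Protocol Table 6, SAP Table 4). Protocol Section 8.3.7 describes a self-rated questionnaire: four questions, each scored 0 to 4, applied to four impulse-control disorders and three related disorders. The same section says of the scale: "It can also be used to monitor changes in symptom severity over time".

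For the analysis, Protocol Section 9.4.5 states: "The CSSRS parameters and QUIP-RS scores will be summarized descriptively by scheduled visit". SAP Section 4.6.3.6 describes the scores as "conducted at Baseline and Week 17 will be summarized at each visit for 4 ICDs", and adds the three related disorders and the total. The default statistics for a continuous score come from SAP Section 4.1: the number of participants with data, then "mean, standard deviation (SD), median, minimum (min) and maximum (max". SAP Section 4.6.3.6 also promises participant-level output: "A listing will be created for all individual questions", together with the domain and total scores.

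The SAP text names two time points, "conducted at Baseline and Week 17". SAP Table 7 maps a further QUIP-RS value after treatment: "Nominal SFU visit [weight and QUIP-RS only".

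**The concern.** The safety question for QUIP-RS concerns individuals: does anyone on suvecaltamide develop impulse-control behaviour, or get worse, and does this happen more often than on placebo? A table of observed scores by visit answers a different question, namely where each arm's distribution lies at each visit. It does not pair a participant's later score with that participant's baseline, and it does not count those who rise. A few sizeable individual increases are averaged with everyone else's scores, and a chance baseline difference between arms carries through to the Week 17 row.

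At stake is how a named safety endpoint is read, and nothing in the efficacy analysis. The listing would contain the information, but the reader would have to pair the scores and compare the arms by hand, with no rule fixed in advance for what counts as worsening.

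**Working it through.** The plan states no figure for QUIP-RS, so there is none to reproduce. The check sets the planned outputs side by side and then does one dilution calculation.

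**1. What each measure gets**

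| Measure | Change from baseline | Count or shift by participant | Source |
|---|---|---|---|
| Vital signs | yes | markedly abnormal values | Protocol 9.4.5; SAP 4.6.3.4, Table 8 |
| Weight | yes | 10% change either way | Protocol 9.4.5; SAP Table 8 |
| ECG | yes | QT thresholds and increases | Protocol 9.4.5; SAP 4.6.3.7 |
| Laboratory values | yes | shift tables | Protocol 9.4.5; SAP 4.6.3.3 |
| Exploratory patient-reported outcomes | yes, to Week 17 | none stated | SAP 4.5.3 |
| QUIP-RS | none stated | none stated | Protocol 9.4.5; SAP 4.6.3.6 |

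**2. Who is in the rows.** SAP Table 7 maps QUIP-RS to Week 17 from Day 36 onward. Any QUIP-RS taken after dosing but before Day 36, other than at a Safety Follow-up visit, has no post-baseline window. A participant who stops during titration can therefore be in the Baseline row and absent from the Week 17 row.

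**3. The adverse-event route.** Protocol Appendix 4 counts newly detected conditions and exacerbations of existing ones as adverse events. SAP Section 4.6.2 tabulates all TEAEs by actual treatment, system organ class and preferred term, with no frequency floor. A case recorded as an adverse event is therefore counted by arm. The link from questionnaire to adverse event is missing, however. Protocol Section 8.3.6 requires a positive post-baseline C-SSRS to be recorded as an adverse event, and Section 8.3.7 has no such rule for QUIP-RS. The adverse events of special interest in SAP Section 4.6.2 are hallucination and syncope. Protocol Section 8.4.2 prefers open-ended, non-leading questions, which need not elicit impulse-control behaviour.

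**4. Dilution (illustrative).**
- Scale, derived from Protocol Section 8.3.7: 4 questions × 4 points = 16 per domain; 7 domains × 16 = 112 in total.
- n = 64 per arm, borrowed from the evaluable number in SAP Section 5. That number was set for the primary endpoint; having the same number with QUIP-RS is an assumption.
- Assumed: k = 4 new cases on suvecaltamide, each rising d = 8 points.
- Shift in the arm mean = k × d / n = 4 × 8 / 64 = 0.5 points out of 112.
- Standard error of the difference between arms = SD × √(2/64). For an assumed SD of 5, 8 or 12 this is 0.88, 1.41 or 2.12, so the shift is 0.57, 0.35 or 0.24 standard errors.
- As a count, the same cases are 4/64 = 6.25% (exact 95% CI 1.7% to 15.2%).

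**5. Which added summary helps (illustrative).** Simulations of the total score assumed half of participants at zero, the rest skewed with mean 10, and retest noise with SD 2. The table gives how often each summary failed to show suvecaltamide as worse.

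| Summary | Failed to show the excess |
|---|---|
| Observed mean (as planned) | about 35% to 37% |
| Mean change from baseline | about 4% to 6% |
| Count rising 8 or more points | about 2% |
| Count with any increase | about 35% to 36% |
| Count going from 0 to above 0 | about 42% to 44% |

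With noise SD 4, the observed mean failed in 35%, mean change in 19%, and a count of rises of 6 or more in 18%. The advantage thus shrinks as noise grows, but the order holds. On the total score, only change from baseline and a count of large rises do better than the planned mean.

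**The case against.** The strongest reply is that impulse-control harm is already covered. TEAE tables count recorded cases by arm. The SAP summarises each of the seven domains separately and reports the maximum, every item and summary score is listed, and safety analyses are descriptive throughout. The protocol's risk section names no impulse-control signal. Dilution over the total also overstates the problem for the domain tables: if all four cases fell in one 0 to 16 domain where 80% to 90% of participants score zero, the observed domain mean would fail to show the excess in only about 0.2% to 11% of simulated trials.

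Much of this stands. A reader might infer that new cases would show in no by-arm table at all. The documents do not support that, because a case recorded as an adverse event appears in the TEAE tables and a very high score can appear in the maximum. What remains is worsening that only the questionnaire picks up. Cases spread over several domains are again harder to see in domain means. The maximum is unreliable too: in one run of the total-score scenario it was no higher on suvecaltamide in 48% of trials, because a new case starting from zero seldom exceeds existing high scorers.

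Unequal numbers at baseline and later visits are normal in a by-visit table, and Table 7 does bring in values from Day 36 for participants who never enter maintenance. That is a reason to pair the values, not a defect in itself.

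**Conclusion.** The point holds in a limited form. For a named safety endpoint, neither document plans within-participant change or a by-arm count of worsening, and the gap concerns worsening seen only on the self-rated scale. It is minor: it adds to descriptive tables and affects no primary or key secondary inference.

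That the two summaries are absent rests on the text alone. The sizes do not: the documents give no QUIP-RS standard deviation, distribution, event rate or cut-off, so the 0.5-point shift and the simulated percentages are illustrations. They should not be read as the chance that this trial misses a signal. A count would not settle the matter either: 4 of 64 against 0 of 64 gives a Fisher p-value of 0.12. Its use is to make the cases visible side by side.

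A reader might also infer that a collected Safety Follow-up QUIP-RS is being discarded. The documents show only that SAP Section 4.6.3.6 and SAP Table 7 disagree. The position of the later QUIP-RS marks in the protocol's Schedule of Activities could not be read reliably from the text available here, so whether that value is collected should be confirmed there.

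**What to change.** In SAP Section 4.6.3.6, with a matching phrase in Protocol Section 9.4.5, add by arm for each of the seven domains and for the total:

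1. Change from baseline in participants with both values.
2. Number and percent with a sizeable increase from baseline at any post-baseline QUIP-RS, including values taken before Day 36. Fix the size bands before unblinding, since the documents give no cut-off. On the total score, do not rely on any increase or on a move from 0 to above 0; under the assumptions above, neither did better than the observed mean.

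Then reconcile the two time points named in Section 4.6.3.6 with the Safety Follow-up value in SAP Table 7, and use that value if it is collected.

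The cost is some SAP wording and one more descriptive table. No new assessment is needed. The downside is a number of low-count cells that need cautious reading.

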9.4.6. Other Analyses

Subgroup analyses and additional analyses of secondary and exploratory endpoints will be further described in the SAP.

9.5. Interim Analysis

No interim analysis will be performed.

10. SUPPORTING DOCUMENTATION AND OPERATIONAL CONSIDERATIONS

10.1. Regulatory, Ethical, and Study Oversight Considerations

10.1.1. Regulatory and Ethical Considerations

- This study will be conducted in accordance with the protocol and with the following:
 - Consensus ethical principles derived from international guidelines including the Declaration of Helsinki and Council for International Organizations of Medical Sciences International Ethical Guidelines;
 - Applicable ICH Good Clinical Practice (GCP) Guidelines; and
 - Applicable laws and regulations.
- The protocol, protocol amendments, ICF, IB, and other relevant documents (eg, advertisements) must be submitted to an IRB/IEC by the investigator and reviewed and approved by the IRB/IEC and national regulatory authority (as applicable) before the study is initiated.
- Protocols and any amendments to the protocol will require IRB/IEC and national regulatory authority approval (as applicable) prior to initiation, except for changes necessary to eliminate an immediate hazard to study participants.
- The investigator will be responsible for the following:
 - Providing written summaries of the status of the study to the IRB/IEC annually or more frequently in accordance with the requirements, policies, and procedures established by the IRB/IEC;
 - Notifying the IRB/IEC of SAEs or other significant safety findings as required by IRB/IEC procedures; and
 - Providing oversight of the conduct of the study at the site and adherence to requirements of 21 CFR, ICH guidelines, the IRB/IEC, EU regulation 536/2014 for clinical studies, and all other applicable local regulations.

10.1.2. Financial Disclosure

Investigators and sub-investigators will provide the sponsor with sufficient, accurate financial information as requested to allow the sponsor to submit complete and accurate financial certification or disclosure statements to the appropriate regulatory authorities. Investigators are responsible for providing information on financial interests during the study and for 1 year after completion of the study.

10.1.3. Informed Consent Process

- The investigator or his/her representative will explain the nature of the study to the participant and answer all questions regarding the study.

- Participants must be informed that their participation is voluntary. Participants will be required to sign a statement of informed consent that meets the requirements (as applicable) of 21 CFR 50, local regulations, ICH guidelines, Health Insurance Portability and Accountability Act requirements, General Data Protection Regulation, and the IRB/IEC or study center.
- The medical record must include a statement that written informed consent was obtained before any study activities were performed unless otherwise allowed by protocol criteria, and must also include the date the written consent was obtained. The authorized person obtaining the informed consent must also sign the ICF.
- Participants must be re-consented to the most current version of the ICF(s) during their participation in the study.
- A copy of the ICF(s) must be provided to the participant.
- Participants who are rescreened are required to sign a new ICF.

10.1.4. Data Protection

- Participants will be assigned a unique identifier by the sponsor. Any participant records or datasets that are transferred to the sponsor will contain the identifier only; participant names or any information that would make the participant identifiable will not be transferred.
- The participant must be informed that his/her personal study-related data will be used by the sponsor in accordance with local data protection law. The level of disclosure must also be explained to the participant who will be required to give consent for their data to be used as described in the informed consent.
- The participant must be informed that his/her medical records may be examined by Clinical Quality Assurance auditors or other authorized personnel appointed by the sponsor, by appropriate IRB/IEC members, and by inspectors from regulatory authorities.

10.1.5. Committee Structure

Establishing a Data Monitoring Committee is not planned for this trial. The sponsor recognizes the importance of ongoing review of the accumulating safety data and will perform periodic data monitoring regularly by data listing review. In addition, safety data from the study will be reviewed on an ongoing basis as part of routine pharmacovigilance and safety surveillance activities. Reports of safety findings (from either single events or based on aggregate review) that suggest a significant risk to humans will be distributed to all participating investigators and to the relevant regulatory authorities and IRBs/IECs.

10.1.6. Dissemination of Clinical Study Data

As the sponsor of the study, Jazz Pharmaceuticals is solely responsible for disclosing results on ClinicalTrials.gov and other public registries in accordance with applicable global laws and regulations. By signing this protocol, the investigator acknowledges that all posting requirements

are solely the responsibility of the sponsor, and he/she agrees not to submit any information about the study or its results.

10.1.7. Data Quality Assurance

- Investigators and site staff will be trained on protocol procedures and eCRF completion prior to enrolling participants in the study.
- All participant data relating to the study will be recorded on printed or eCRF unless transmitted to the sponsor or designee electronically (eg, laboratory data). The investigator is responsible for verifying that data entries are accurate and correct by physically or electronically signing the CRF.
- Guidance on completion of CRFs will be provided in the CRF completion guidelines.
- The investigator must permit study-related monitoring, audits, IRB/IEC review, and regulatory agency inspections and provide direct access to source data documents.
- Monitoring details describing strategy (eg, risk-based initiatives in operations and quality such as Risk Management and Mitigation Strategies and Analytical Risk-Based Monitoring), methods, responsibilities and requirements, including handling of noncompliance issues, and monitoring techniques (central, remote, or on-site monitoring) are provided in the Monitoring Plan.
- The sponsor or designee is responsible for the data management of this study, including quality checking of the data.
- The sponsor assumes accountability for actions delegated to other individuals (eg, Contract Research Organizations).
- Records and documents, including signed ICFs, pertaining to the conduct of this study must be retained by the investigator or institution/site as applicable, for the period established in the clinical study agreement entered into by the investigator's study site unless local regulations or institutional policies require a longer retention period. No records may be destroyed during the retention period or thereafter without the written approval of the sponsor. No records may be transferred to another location or party without written notification to the sponsor.

10.1.8. Source Documents

- Source documents provide evidence for the existence of the participant and substantiate the integrity of the data collected. Source documents are filed at the investigator's site.
- Data reported on the CRF or entered in the eCRF that are transcribed from source documents must be consistent with the source documents or the discrepancies must be explained. The investigator may need to request previous medical records or transfer records, depending on the study. Also, current medical records must be available.
- Definition of what constitutes source data can be found in the Monitoring Plan and/or CRF completion guidelines.

- The investigator must maintain accurate documentation (source data) that supports the information entered in the CRF.
- Study monitors will perform ongoing source data verification to confirm that data entered into the CRF by authorized site personnel are accurate, complete, and verifiable from source documents; that the safety and rights of participants are being protected; and that the study is being conducted in accordance with the currently approved protocol and any other study agreements, ICH GCP, and all applicable regulatory requirements.

